7.4.3 Potential Medication Interactions

Iron-drug interactions of clinical significance have been reported to occur with a large number of concomitant therapies. Concurrent ingestion of oral iron causes marked decrease in the bioavailability of a number of drugs due to the formation of iron-drug complexes (chelation or binding of iron by the second drug). Examples of affected drugs are: quinolone or tetracycline antibiotics, bisphosphonates, angiotensin-converting enzyme inhibitors, folic acid, methyldopa, levodopa, carbidopa, levothyroxine, and mycophenolate.

To minimise the potential for drug interactions, Ferric Maltol should be taken on an empty stomach at least 2 hours prior to other concomitant medications and/or supplements.

7.5 INDIVIDUAL DISCONTINUATION CRITERIA

Subjects and/or their parents or guardians have the right to withdraw consent without prejudice at any time during the study. If a subject withdraws consent, the Investigator should make a reasonable effort to determine the cause. All withdrawn subjects should have a Post-Study Visit within 3-10 days after the last dose of study drug (if the subject agrees in the case of withdrawn consent).

Subjects may be discontinued prematurely during the study for the following reasons:

- Withdrawal of informed consent.
- Unwillingness or inability to comply with protocol requirements.
- Pregnancy or not using a reliable method of birth control (female subject of childbearing potential, if applicable).
- Use of prohibited concomitant medications.
- Serious adverse events that are judged by the Investigator to be related to Ferric

Maltol.

The reason for study drug discontinuation and the date of last dose should be recorded in the eCRF. Subjects who discontinue treatment prematurely must return for the Post-study visit, unless informed consent is withdrawn (and the subject and/or their parents or guardians do not agree to attend this visit follow-up visit).

7.6 STUDY TERMINATION

The Sponsor reserves the right to temporarily halt and/or terminate the study (or if appropriate, individual treatment dose groups) at any time for safety, scientific or ethical reasons including, but not limited to:

- Emerging safety concerns from this study, other ongoing studies with Ferric Maltol, or new and relevant scientific information, which result in the risk-benefit ratio for this study becoming unfavorable, in the Sponsor's opinion.
- If the total number of dropouts is so high or the number of included subjects is so low that completion of the trial will not realistically be expected within a reasonable timeframe.
- If the Sponsor determines the study will no longer reveal new knowledge and consequently is ethically no longer justifiable.

In case of an early termination of the study or temporary halt by the Sponsor, the IEC and CA will be notified within 15 calendar days, including a detailed written explanation of the reasons for the termination/halt.

In all circumstances connected with temporary halt and/or termination of the study, the following principles will apply:

- All affected parties (such as the IEC, CA, Investigators, heads of study centres/clinic directors) must be informed as applicable according to local law.
- All study materials and supplies (except documentation that should remain stored at site) must be returned to the Sponsor/designee.

8 TREATMENT OF SUBJECTS

Ferric Maltol will be supplied to study sites on behalf of Shield TX (UK) Ltd by Piramal Healthcare UK Limited, [name]. The drug substance and drug product are manufactured, tested and controlled in accordance with Good Manufacturing Practice (GMP). Full details are documented in the Investigational Medicinal Product Dossier (IMPD) and current Investigator's Brochure. Sites must arrange storage of Investigational Medicinal Product in a temperature monitored, secure location which is accessible to authorised individuals only.

8.1 INVESTIGATIONAL MEDICINAL PRODUCT (IMP) PRESENTATION

Ferric Maltol is presented as a hard, gelatine, red capsule. For the purposes of this study capsules containing three different doses of iron and associated excipients will be provided:

- 30 mg capsule: Each capsule contains 30 mg iron and the following excipient(s) with known effect: lactose, Allura Red AC (E129) and Sunset Yellow FCF (E110).
- 16.6 mg capsule: Each capsule contains 16.6 mg iron and the following excipient(s) with known effect: lactose, Allura Red AC (E129) and Sunset Yellow FCF (E110).
- 7.8 mg capsule: Each capsule contains 7.8 mg iron and the following excipient(s) with known effect: lactose, Allura Red AC (E129) and Sunset Yellow FCF (E110).

A full list of excipients can be found in the Investigator's Brochure.

8.2 PACKAGING

Ferric Maltol capsules will be supplied in white polypropylene securitainer with a tamper evident standard securitainer cap of white medium density polyethylene. A single bottle containing 56 capsules will be provided to cover the entire 10-day treatment duration of the study for each subject. Each bottle will be uniquely numbered to facilitate allocation to an individual subject at randomisation.

8.3 STORAGE

IMP must be stored below 25 °C and must not be refrigerated or frozen. In the event that the drug is exposed to temperatures greater than or equal to 25°C, the CRA/Sponsor should be contacted for review and further instruction.

8.4 LABELLING

All bottles will be identified by a unique Bottle ID number. Bottles will be clearly labelled as Ferric Maltol with the dose indicated. Labels of the IMP will contain information according to European Directives 2003/94/EC, 2001/20/EC and Annex 13.

Individual supplies packaging and labelling will be checked by the Investigator/designee before the subject takes their first dose of study medication at site on Day 1, after which subjects will take their medication home and continue dosing from Day 1 evening, then

morning and evening from Days 2 to 9. The subject should withhold their morning dose on Day 10 until attending the site for PK assessments. The final single dose will be taken under supervision at the study site on the morning of Day 10, after pre-dose PK blood samples have been collected.

8.5 DISPENSATION

A specific strength bottle will be allocated to each subject according to the Ferric Maltol treatment randomly allocated for the 10-day dosing period using the eCRF system. Sites will dispense the next available bottle ID number for the corresponding Ferric Maltol dose group to each individual subject. Full details will be provided to sites in the Pharmacy File for the study.

8.6 ADMINISTRATION

Eligible subjects will be randomly allocated to one of the three Ferric Maltol dose groups according to a centralised treatment allocation scheme in the eCRF, as follows:

1. Group 1 – 12 subjects will receive 30 mg Ferric Maltol twice daily for 9 days (Days 1-9) plus a final 30mg dose on the morning of Day 10. PK study Day 1 & Day 10.
2. Group 2 – 12 subjects will receive 16.6 mg Ferric Maltol twice daily for 9 days (Days 1-9) plus a final 16.6mg dose on the morning of Day 10. PK study Day 1 & Day 10.
3. Group 3 – 12 subjects will receive 7.8 mg Ferric Maltol twice daily for 9 days (Days 1-9) plus a final 7.8mg dose on the morning of Day 10. PK study Day 1 & Day 10.

Subjects should be instructed to take Ferric Maltol on an empty stomach (one hour before eating, or two hours after eating) with a glass of water, as the absorption of iron is reduced when taken with food. The capsules should be swallowed whole only.

The first capsule of Ferric Maltol will be administered in the presence of the site staff on Day 1. For subsequent doses, depending upon the age of the subject, capsules may need to be administered under the supervision of the child's parent or guardian. Subjects will be instructed to withhold their final dose of Ferric Maltol on the morning of Day 10 until pre-dose PK blood samples have been collected at the site.

If a subject forgets to take a dose he/she should take the next dose as normal. The subject should not take a double dose to make up for a forgotten capsule.

8.7 TREATMENT COMPLIANCE

Subjects will be instructed to take the study drug as described in detail on the drug labels and by the Investigator/designee. Subjects will be given a Diary Card on Day 1 after first dosing with Ferric Maltol at the study site and will be instructed to complete this card daily from the evening of Day 1 until the evening of Day 9, in order to document the day and time that they

took their morning and evening doses of Ferric Maltol on those treatment days whilst at home. Subjects will be instructed to return all unused supplies and all clinical study medication packaging on the morning of Day 10, having withheld their dose of Ferric Maltol that morning. Compliance will be assessed from the Diary Card entries and unused capsule count.

The delivery of medication to the site, its use and return, as well as subject-specific compliance, will be reconciled and documented using a Drug Accountability Form in order to monitor compliance with the medication schedule. All opened containers, together with remaining contents, and unopened containers will be kept by the Investigator in a secure, locked area until return to the drug supplier by the monitor or destruction by the site if agreed with the Sponsor/designee. The Investigator will use the IMP only within the framework of this clinical study and in accordance with the current, approved study protocol.

8.8 CONTINUATION OF TREATMENT

No further provisions are made for access to the study treatment under this protocol following Visit 3, Day 10.

9 ENROLMENT AND RANDOMISATION PROCEDURES

Full details of procedures will be provided in the Investigator Site File and eCRF Completion Guidelines.

9.1 SCREENING

Subjects will be evaluated according to the inclusion and exclusion criteria (Sections 7.3.1 and 7.3.2). Subjects will be deemed eligible for randomisation if all inclusion criteria and no exclusion criteria are met. The Investigator is required to document all screened candidates considered for inclusion in this study. If excluded prior to randomisation, the reasons for exclusion will be documented in the subject's eCRF, medical notes and on the study screening log.

A subject may be retested once for screening laboratory criteria that do not meet protocol in/exclusion criteria initially, so long as randomisation occurs no more than 14 days from the initial Screening visit date (if eligible based on retest results).

9.2 RANDOMISATION

Subjects will be registered into the study at the Screening visit and assigned a unique subject identification number in the eCRF. Subjects will be categorised during the screening process based upon their age (10 to 14 years of age and 15 to \leq 17 years of age) and their gender. Age and gender will be incorporated into the randomisation as stratification factors. This will ensure that a minimum of 25% of each gender and at least 3 children per age group (15-17 yrs and 10 to 14 yrs) are enrolled and treated in each Ferric Maltol dose group.

A final eligibility evaluation must be conducted by the Investigator/designee prior to randomisation in the eCRF system, once the results of all Screening assessments are available. No subject may begin Ferric Maltol treatment prior to being randomised in the eCRF system. The randomisation procedure (created using a computer generated random permutation procedure) will assign the subject to one of the three study treatment groups (Ferric Maltol 30 mg, 16.6 mg or 7.8 mg BID). The randomisation process will also specify which PK blood sampling schedule should be followed for an individual subject on Day 1 and Day 10, in order to ensure that the minimum of three subjects per age group and Ferric Maltol dose group have PK samples collected at each of the required time point windows (see Section 10.7.2).

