9.3 REPLACEMENT POLICY

Discontinuations after randomisation due to adverse events will not be replaced. Discontinuations after randomisation for any other reasons may be replaced at the discretion of the Sponsor, in order to reach the agreed number of evaluable subjects for pharmacokinetic endpoints.

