10.7.3 Urine Pregnancy Test

Females of childbearing potential only. A urine pregnancy test should be conducted at the Screening visit to assess eligibility using the test kits provided by the central laboratory. A repeat urine pregnancy test will be conducted prior to first dosing with Ferric Maltol on Day 1; the result of this test must be negative for dosing with Ferric Maltol to commence on Day 1. Repeat urine pregnancy testing will also be conducted on Day 10 and at the Post-study visit.

Full details of the required sample collection and processing procedures will be described in the study-specific Laboratory Manual.

10.7.4 Summary table of sparse PK blood sampling schedule on Day 1 and Day 10

On PK study Days 1 and 10, all subjects will have baseline (pre-dose) PK blood samples collected immediately prior to Ferric Maltol dosing (0h). Subjects will then have further PK blood samples collected at two (2) additional times between 0.5h and 6h after dosing on Days 1 and 10; within each Ferric Maltol dose group (7.8mg 16.6mg or 30mg BID), the post-dose PK sample time collection windows will be 0.5-1h, 1.0-2.0h, 2.0-3.0h, 3.0-4.0h and 4.0-6.0h. The twelve (12) subjects within each Ferric Maltol dose group will be assigned to the required post-dose PK blood sampling schedule in sequential order at the time of

randomisation, based on current subject enrolment across all study sites. This is summarised in the following table:

PK Sample Schedule Day 1 and Day 10	PK Sample Schedule Group 1 (N=3/12)	PK Sample Schedule Group 2 (N=3/12)	PK Sample Schedule Group 3 (N=3/12)	PK Sample Schedule Group 4 (N=3/12)
Pre-dose (0h)	X	X	X	X
0.5 – 1 hour	X	X		
1 – 2 hours	X		X	
2 – 3 hours		X		X
3 – 4 hours			X	
4 – 6 hours				X

For each individual subject, the post-dose PK blood sampling schedule will be the same on Day 1 and Day 10. Post-dose samples for each subject must be collected within the allocated time-windows (e.g. Between 0.5-1h or 1-2h); the exact time of sample collection will be recorded in the eCRF. For those subjects in PK Sample Schedule Group 1 (see above table), the PK blood samples for the 0.5-1h timepoint window should be taken at 30 minutes before the PK blood samples for the 1-2h timepoint window on Day 1 and Day 10, to provide an adequate spread of actual sampling times for the population PK analysis.

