4.2 Primary Pharmacokinetic Measurements and Variables

4.2.1 PK blood sampling

On study days 1 and 10, all subjects were to have baseline (pre-dose) PK blood samples collected immediately prior to Ferric Maltol dosing (0h). Subjects were then to have further PK blood samples collected at two additional times between 0.5h and 6h after dosing on Days 1 and 10; within each Ferric Maltol dose group (7.8 mg, 16.6 mg or 30 mg BID), the post-dose PK sample time collection windows were 0.5-1h, 1.0-2.0h, 2.0-3.0h, 3.0-4.0h and 4.0-6.0h. The 12 subjects within each Ferric Maltol dose group were assigned to the required post-dose PK blood sampling schedule in sequential order at the time of randomisation, based on current subject enrolment across all study sites. Table 3 details the sparse PK blood sample schedule.

Table 3 Sparse PK Blood Sampling Schedule

	PK Sample Schedule			
	Group 1 (N = 3/12)	Group 2 (N = 3/12)	Group 3 (N = 3/12)	Group 4 (N = 3/12)
Pre-dose (0h)	X	X	X	X
0.5 – 1h	X	X		
1.0 – 2.0h	X		X	
2.0 – 3.0h		X		X
3.0 – 4.0h			X	
4.0 – 6.0h				X

For each individual subject, the post-dose PK blood sampling schedule was to be the same on Day 1 and Day 10. Post-dose samples for each subject were to be collected within the allocated time-windows (e.g. between 0.5-1h or 1-2h); the exact time of the sample collection was to be recorded in the eCRF. For those subjects in PK Sample Schedule Group 1 (see Table 3), the PK blood samples for the 0.5-1h timepoint window were to be taken at 30 minutes prior to the PK blood samples for the 1-2h timepoint window on Day 1 and Day 10, to provide an adequate spread of actual sampling times for the population PK analysis.

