7 ANALYSIS OF DISPOSITION AND SUBJECT CHARACTERISTICS

7.1 Disposition and Analysis Populations

Subject disposition will be presented for all subjects in the Screened Population. The number and percentage of subjects who meet each of the following categories will be summarised by dose group and overall, as appropriate:

- Screened;
- Screen success;
- Screen failure and reasons for screen failure;
- Dosed;
- Complete the open-label treatment period; and
- Prematurely discontinue during the open-label treatment period and reasons for study discontinuation.

Subjects who screen fail will be listed detailing date of screen failure and primary reason for screen failure.

The number of subjects in the Screened Population, Dosed Group, Safety Population, and FAS/ITT Population will be tabulated by dose group and overall. A listing of analysis population inclusion will also be provided.

Inclusion/Exclusion criteria deviations will be listed and summarized for the Dosed Group and those excluded from the Screened Population.

All available visit dates will be listed for the Screened Population.

A listing of informed consent will be provided for the Screened Population. This listing will contain the date of informed consent (for the subject and/or parent/guardian) and the protocol version to which informed consent was provided; details of reconsent, as appropriate, will also be included.

Treatment details will be listed for the FAS/ITT Population and will contain, for each subject, details of the stratification variables (gender and age group), date of randomization, randomization number, the dose group the subject was randomised/assigned to ('Planned') and the dose the subject actually received ('Actual'), the date of first dose of study drug and the PK Sampling Group the subject was allocated to.

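### Protocol 9.2 promises three subjects per age group and dose group in every PK window, but the sampling table has too few slots: 24 per dose group against 30 needed

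*Protocol*

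**What the plan says.** Protocol 9.2 sets an enrolment floor: "at least 3 children per age group (15-17 yrs and 10 to 14 yrs) are enrolled and treated in each Ferric Maltol dose group". It then says the randomisation process also fixes each subject's PK sampling schedule, so as to ensure that a "minimum of three subjects per age group and Ferric Maltol dose group have PK samples collected at each of the required time point windows".

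Protocol 10.7.4 gives the schedules. After the pre-dose sample, each subject has "further PK blood samples collected at two (2) additional times between 0.5h and 6h after dosing". There are five post-dose windows and four schedules, with three of the 12 subjects in a dose group on each schedule. A subject keeps the same schedule on Day 1 and Day 10. Subjects "will be assigned to the required post-dose PK blood sampling schedule in sequential order", according to current enrolment across sites. SAP 4.2.1 and its Table 3 repeat this: subjects "were assigned to the required post-dose PK blood sampling schedule in sequential order at the time of randomisation, based on current subject enrolment". Neither section mentions age in the schedule assignment. Protocol 9 adds that "Full details of procedures will be provided in the Investigator Site File and eCRF Completion Guidelines"; those documents were not available for this review.

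**The concern.** Section 9.2 presents age-by-dose-by-window coverage as something the allocation secures. Each subject gives only two post-dose samples over five windows, and the two latest windows each appear in a single schedule of three subjects. A minimum of three in each of two age groups cannot come from three subjects.

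Age is a candidate covariate in the population model (SAP 8.5.3, where applicable), and a reader would take 9.2 as assurance that both age groups are observed across the whole profile at each dose. The late windows matter most for serum iron and TSAT, which are primary endpoints: Protocol 5.4 reports adult serum iron on 30 mg still 11.8 umol/L above baseline at 6 h on Day 1. For maltol and its glucuronide the stake is small, since their adult half-lives are about 1 h (0.8 h and 1.1 h) and the 2-3 h window already informs elimination.

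**Working it through.** **Inputs.** Two age groups, 10-14 and 15-17 years (Protocol 7.1, 9.2). Twelve subjects per dose group, two post-dose samples per subject per PK day, five windows, four schedules of three subjects (Protocol 10.7.4, SAP Table 3). Required minimum: three (Protocol 9.2).

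**Slots supplied and needed, per dose group per PK day.** On the joint reading each window needs 2 x 3 = 6.

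| Window | Schedules that sample it | Subjects | Needed | Short by |
|---|---|---|---|---|
| 0.5-1 h | 1, 2 | 6 | 6 | 0 |
| 1-2 h | 1, 3 | 6 | 6 | 0 |
| 2-3 h | 2, 4 | 6 | 6 | 0 |
| 3-4 h | 3 | 3 | 6 | 3 |
| 4-6 h | 4 | 3 | 6 | 3 |
| Total | | 24 | 30 | 6 |

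Day 10 adds no subjects, because schedules do not change between days. Even the first three windows reach the minimum only with an exact 3:3 age split.

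**Without the table.** At the enrolment floor, an age group has three subjects in a dose group. They give 3 x 2 = 6 post-dose samples a day; three in each of five windows needs 3 x 5 = 15.

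**Best achievable.** I enumerated all 4^4 = 256 ways of dividing the three subjects on each schedule between the two age groups. The largest number of the 10 age x window cells that can reach three is:

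| Age split in the arm | 3:9 | 4:8 | 5:7 | 6:6 | 7:5 | 8:4 | 9:3 |
|---|---|---|---|---|---|---|---|
| Cells reaching three (of 10) | 7 | 6 | 6 | 8 | 6 | 6 | 7 |

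No split lifts the smallest cell above one subject.

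**Size of the gap.** With the four existing schedules, an age group within a dose group needs at least three on schedule 3 (for 3-4 h), three on schedule 4 (for 4-6 h) and three on schedules 1 and 2 together (for 0.5-1 h), so nine. That is 9 x 2 x 3 = 54 subjects against 36. This measures the gap; it is not a proposal.

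**Weaker reading: separate minima.**
- Three per dose group per window: the smallest count is 3, so this is met exactly, given 12 per arm and complete sampling.
- Three per age group per window, pooled over doses: each late window holds 3 x 3 = 9 subjects against 6 needed. This is possible but not secured. If schedules fall at random with respect to age, the number from an age group of size k in one late window is hypergeometric (36, k, 9). The probability that either age group has fewer than three is:

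| Smaller age group, of 36 | In a given late window | In at least one of the two |
|---|---|---|
| 18 | 12% | 22% |
| 15 | 18% | 34% |
| 12 | 35% | 63% |
| 9 (three per arm, the lowest 9.2 allows) | 60% | 90% |

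These figures show what the described assignment leaves open. They are not forecasts, because 9.2 does state an aim by age.

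**The case against.** **It does not matter much.** Observed data are summarised by dose group and timepoint (SAP 8.4), parameters come from model-predicted individual profiles (SAP 8.5.4), there is no formal sample size calculation to upset (SAP 13), and an age effect is estimated across all doses, windows and both days. Nothing in the SAP uses the 9.2 minimum. This stands, and it is why the consequence is modest. It does not make the statement true.

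**Another reading is available.** The phrase could refer back to the three children per age group required at enrolment and mean that, between them, they cover the windows. Schedules 3, 4 and 1 do cover all five windows with three subjects. But the wording asks for three subjects at each window, and sequential assignment without regard to age would not secure even this softer version.

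**The mechanism may be described elsewhere.** An age-aware rule may be in the Investigator Site File or the eCRF guidelines. That bears on the pooled reading and on the percentages above. It cannot rescue the joint reading, because no procedure puts six subjects into a window planned for three.

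**Lost subjects can be replaced.** Protocol 9.3 says "Discontinuations after randomisation due to adverse events will not be replaced", but allows replacement for other reasons at the sponsor's discretion. Replacement can restore the planned 12; it does not create the missing slots.

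**Allocation may be finished.** The SAP describes it largely in the past tense, and changing the protocol needs written agreement under Protocol 14.6. This affects where the correction goes, not whether it is needed.

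**Conclusion.** The concern holds. On the joint reading, Protocol 9.2 states a property the design cannot have: 30 samples needed and 24 supplied per dose group per PK day, short by three at 3-4 h and three at 4-6 h, with at most 8 of 10 age x window cells able to reach three. This is a direct count from the documents and rests on no assumption beyond that reading. On the weaker reading, the dose-group minimum is met with no spare subject in the late windows, and the pooled age minimum is possible but not secured by the assignment described.

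The correction should be made, although the effect on the analysis is modest. It is limited to what may be claimed about age coverage, chiefly for late serum iron and TSAT. No loss of precision for any endpoint has been estimated.

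**What to change.** 1. Restate Protocol 9.2 so that schedule allocation is planned to give at least three subjects per dose group in each window, and drop the claim of per-age coverage within dose. Planned is safer than ensured, because the two late windows have no spare subject. If the protocol can no longer be amended, put the corrected statement in the SAP or the clinical study report; SAP 14 currently records no planned changes.
2. Report the achieved age-by-window counts alongside the covariate analysis. SAP 7.1 already lists the age stratum and "the PK Sampling Group the subject was allocated to" for each subject.

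The cost is one sentence, plus the protocol change procedure if that route is used, and one small count table. No extra subjects, samples or visits are needed.

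Optionally, and only if allocation is still open, schedules could be assigned in the order 3, 4, 1, 2 within each dose group and age stratum. Each age group would then reach all five windows once an arm has three of that age. This still does not give the joint property. At a 6:6 age split it changes the window counts from 6, 6, 6, 3, 3 to 4, 6, 6, 4, 4, so it takes samples from 0.5-1 h, in the absorption phase of maltol (adult median Tmax 1.0 h). It is a trade-off and is not needed to resolve the point.
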